- ⁿ Obtained between 4 to 8 hours postdose. The samples may be obtained on Day 4 if necessary due to scheduling difficulties.
- ^o Additional aspirates and biopsies will be collected as clinically indicated (eg, Cycle 1 Day 15 based on Investigator's medical assessment).
- ^p Molecular and cytogenetic studies may be omitted at: Screening, if they were completed within the previous 90 days and the results are available for recording on the electronic case report forms; see Section 6.1 for details on sending samples to the central laboratory.
- ^q Urine PK to be performed on approximately 10 selected subjects from Part A and/or Part B. This is a 24-hour collection that starts C1D1 and ends C1D2.
- ^r RT-PCR testing for SARS-CoV-2 is mandatory within 7 days prior to first dose of CC-90009 (C1D1). The RT-PCR test should be based on institutional or local guidelines. Please see Section 6.1 in the event of a positive result.
- ^s Serum will be collected at predose on Cycle 1 Day 1 (or at screening), approximately every 6 months during study treatment and at EOT to be used for possible measurements of anti-SARS-CoV-2 serology (anti-SARS-CoV-2 total or IgG). Results will not be used to determine eligibility. Serum should also be collected approximately 4 weeks after a documented or suspected SARS-CoV-2 infection.
- ^t Medical history will also include COVID-19 vaccines, toxicities of prior treatments, and known allergies.

Table 7: Table of Events for Cycles ≥ 2 in Part B (D1-5 Schedule), End of Treatment Visit, and Follow-up Period

					Tr	eatment P	eriod				Follow-up Period	
					Cycle	$es \ge 2$						
			WK1			WK2	WK3	v	VK4	EOT ^b	Safety ^c	
Events ^a	Day 1	Day 2	Day 3	Day 4	Day 5	Day 8	Day 15	Day 22	Day 28	\leq 28 days	28 days (± 3 days)	Long Term
Review concomitant medications & procedures (Section 6.2.1)	Х	Х	Х	Х	Х	Х	Х	Х	X	Х	Х	
CC-90009 Administration (Section 7)												
Calcium, calcitriol and Vitamin D supplements and recording on diary card (Section 7.2)	X	Х	Х	X	X ^d	X ^d			$X (C2 and C3)^d$			
Provide/ review of diary card	X									Х		
Corticosteroid administration (dexamethasone) (refer to Section 7.2) for doses 3.6 mg and above	Х	Х	Х	х	Х							
IV administration of CC-90009 ^e	Х	Х	Х	X	Х							
Safety Assessments (Section 6)												
Adverse Event Evaluation (Section 6.2.2)	Х	Х	Х	Х	Х	Х	Х	Х		Х	Х	
Weight (Section 6.2.3)	X									X		
Vital Signs (Section 6.2.3)	Xf	Xf	Xf	Xf	Xf	Х	X	Х		X		
Physical Examination (Section 6.2.4)	Х									Х		
ECOG PS (Appendix D)	Х									X		
12-lead ECG (Section 6.2.5) ^g	X									X		
LVEF (ECHO/MUGA; Section 6.2.6)	$\begin{array}{c} X\\ (only\\ C2 \pm\\ 7d) \end{array}$									$X (\pm 7d)^h$		
Pregnancy test (FCBP only; Section 6.2.7)	Х						X ⁱ			X ⁱ	X ⁱ	

Table 7:	Table of Events for Cycles ≥ 2 in Part B (D1-5 Schedule), End of Treatment Visit, and Follow-up Period
----------	--

					Tr	eatment P	eriod				Follow-uj	p Period
					Cycl	$es \ge 2$						
			WK1			WK2	WK3	W	/K4	EOT ^b	Safety ^c	
Events ^a	Day 1	Day 2	Day 3	Day 4	Day 5	Day 8	Day 15	Day 22	Day 28	≤28 days	28 days (± 3 days)	Long Term
Pregnancy risk counseling and contraceptive compliance confirmation	Х				As	specified ir	n Section 6.1	.1 and the Pl	PP in Appendi	ix L		
Hematology laboratory (Section 6.2.8)	Х	Х	Х	Х	Х	Х	Х	Х		Х		
Serum chemistry laboratory tests (Section 6.2.8) ^j	Х	Х				Х	Х	Х		Х		
Serum Ca & Mg tests (Section 6.2.8) ^j	Xj	Xj	Xj	Xj	Xj							
Serum PTH test (Section 6.2.8)	Х				Х					Х		
Serum P1NP and β-CTx tests (Section 6.2.8)	Х									Х		
Serum 25-hydroxyvitamin D level (Section 6.2.8)	Х											
Urine Ca/ creatinine ratio test (random) (Section 6.2.8)	Х				Х					Х		
Amylase, lipase, T-cell subsets (CD4+ and CD8+), TSH (Section 6.2.8)	Х									Х		
PT, INR, PTT (for subjects on anticoagulant therapy) (Section 6.2.8)	Х									Х		
Urinalysis (Section 6.2.8)	Х									Х		
PK & PD Assessments												
Blood, PK (Section 6.5)°				Xº	Xº							
Blood (whole), PD biomarker (Section 6.6.2)									X (C2 and C4; ± 3d)	X ⁿ		Refer to Section 6.3.2

Table 7: Table of Events for Cycles ≥ 2 in Part B (D1-5 Schedule), End of Treatment Visit, and Follow-up Period

					Tr	eatment P	eriod				Follow-uj	p Period
					Cycle	$es \ge 2$						
			WK1			WK2	WK3	v	VK4	EOT ^b	Safety ^c	
Events ^a	Day 1	Day 2	Day 3	Day 4	Day 5	Day 8	Day 15	Day 22	Day 28	≤ 28 days	28 days (± 3 days)	Long Term
Bone marrow aspirate and biopsy, PD biomarkers & MRD (Section 6.6.3) ^{l, m}									X (C2 and C4; ± 3d)	X ⁿ		Refer to Section 6.3.2
SARS-CoV-2 Serology ^p (Section 6.6.4)		Serum collected every 6 months during study treatment (eg, C6D1, C12D1, etc)						etc)	Х			
Efficacy												
Complete blood counts and examination of peripheral blood smears (Section 6.4) ^m									X (C2 and C4; ± 3d)	X ⁿ		Refer to Section 6.3.2
Bone marrow aspirate and/or biopsy (Section 6.4) ^m									X (C2 and C4; ± 3d)	X ⁿ		Refer to Section 6.3.2
Follow-up												
CC-90009-related AE/SAE follow-up		Refer to Section 6.3.1										
Anticancer therapies		Refer to Section 6.3.2										
Survival		Refer to Section 6.3.3										
Transformation to AML for MDS		After sig	gning ICF	and until	death, lost	to follow-	up, withdraw	al of consen	t for further d	ata collection,	or end of trial	

Abbreviations: Adverse event = AE; AML = acute myeloid leukemia; β -CTx = beta C-terminal telopeptide; C = cycle; Ca = calcium; CD = cluster of differentiation; D = day; ECHO = echocardiogram; ECG = electrocardiogram; ECOG PS = Eastern Cooperative Oncology Group performance status; EOT = End of Treatment; FCBP = females of child bearing potential; INR = international normalized ratio; IV = intravenous; LVEF = left ventricular ejection fraction; MDS = myelodysplastic syndromes; Mg = magnesium; MUGA = multi-gated acquisition scan; P1NP = procollagen type 1 N-terminal propeptide; PD = pharmacodynamic; PK = pharmacokinetic; PPP = pregnancy prevention plan; PT = prothrombin time; PTH = parathyroid hormone; PTT = partial thromboplastin time; q = every; SAE = serious adverse event; SARS-CoV-2 = severe acute respiratory syndrome coronavirus 2; TSH = thyroid-stimulating hormone; WK = week.

^a All study visits/procedures will have a ± 2 day window and all laboratory blood samples should be drawn predose (≤ 5 hrs), unless otherwise specified in this table or Section 6. Cycles should start ≤ 7 days after the last day of the previous cycle.

^b EOT Visit performed within 28 days after last dose of CC-90009 for subjects that discontinue prior to completing dosing in Cycle 4. For subjects that complete dosing in Cycle 4, this visit should be completed on Day 28 (± 2 days) of Cycle 4. For subjects who complete dosing after Cycle 4, EOT Visit should be completed within 28 days after the last day of the previous cycle.

- ^c Safety Follow-up Visit is performed 28 days (± 3 days) after the last dose of CC-90009 for all subjects. May be performed by telephone contact if pregnancy testing is not required (refer to footnote "i").
- ^d Supplements to be administered for at least 3 days after the last dose in each cycle. Supplementation may be prolonged if hypocalcemia occurs (refer to Section 7.2.13.2). Subjects to start supplements at least 3 days prior to Day 1 of Cycles 3 and 4 as per Section 7.2.
- ^e Subjects will be closely monitored during the administration of CC-90009 and for at least 1 hour after. Subjects should be adequately hydrated to prevent potential tumor lysis syndrome (TLS) (eg, 2 to 3 liters of oral or IV fluids per day) starting the day prior to CC-90009 administration and continuing through each day of CC-90009 administration. Refer to Section 7.2.12 for information on dose interruptions. The SRC may decide to evaluate alternate dosing schedules (eg, increasing from 5 to up to 10 consecutive days of CC-90009 administration) based on their review of available clinical and laboratory safety data, PK profiles, and PD findings. Subjects should be administered Cycle ≥ 2 of CC-90009 in a Limited Stay Unit (LSU) or as inpatient. Subjects experiencing Grade ≥ 2 hypocalcemia during any cycle should be administered CC-90009 in the inpatient setting for subsequent cycles (an exception can be made for subjects with grade 2 hypocalcemia lasting less than 24 hours that recovers without IV calcium [eg, calcium gluconate or calcium chloride] after discussion with the Celgene medical monitor).
- ^f Multiple measurements performed on this day. For subjects who are administered as in-patient in Cycles ≥ 2 , on days that CC-90009 is administered, vital signs will be obtained prior to dosing (≤ 3 hours), and 60 minutes (± 15 minutes) and 6 hours (± 1 hr) after the end of the administration of the dose. Starting in Cycle 2 in the outpatient setting, vital signs will be obtained prior to dosing (≤ 3 hours) and at 60 minutes (± 15 minutes) after the end of the administration of the dose. Additional vital signs should be obtained as clinically indicated per the Investigator's medical assessment.
- ^g Triplicate ECGs will be performed on Day 1 of each cycle (refer to Section 6.2.5) and a single ECG obtained at the EOT visit.
- ^h The EOT Visit LVEF is not required if the prior LVEF was performed within 56 days.
- ⁱ Per the PPP, a pregnancy test is required 28 days after the last dose of for all FCBP. For FCBP with irregular menstrual periods, a pregnancy test is required every 14 days (ie, Day 15 of Cycles ≥ 2 and at 14 and 28 days after the last dose of CC-90009).
- ^j In the event of Grade ≥ 2 hypocalcemia or symptoms of hypocalcemia (eg, carpopedal spasm, tetany, seizures, etc), subjects must be hospitalized. Also, if Grade ≥ 2 hypocalcemia and abnormal levels of serum albumin occurs, a serum ionized calcium test must be performed. Refer to Section 7.2.13.2 for hypocalcemia management guidelines. Refer to Section 6.2.8 for required days and timing of tests. Subjects who experienced Grade ≥ 2 hypocalcemia during Cycle 1, require testing Days 1-5 at 6 and 12 hours postdose. All other subjects require testing prior to dosing.
- ^k If intra-subject dose escalation occurs, blood samples for PD assays will be collected during the first cycle only at the increased dose; see laboratory manual for details. Multiple blood samples will be collected for this assay on the specified Days 1, 2, 5. Refer to Section 6.6.
- ¹ Bone marrow samples for biomarker PD assessment are mandatory. When applicable (refer to time points in the table above), bone marrow samples for biomarker PD assessment will be obtained at the same time as a scheduled efficacy assessment. If sufficient bone marrow aspirate specimen is not available, peripheral blood may be submitted in place of the BMA specimen for biomarker studies (eg, MRD); see laboratory manual for details. A bone marrow biopsy can be collected in conjunction with an aspirate if it is standard institutional practice. A bone marrow biopsy must be collected if adequate aspirate sample is not attainable; see for details on sending samples to the central laboratory for disease assessment.
- ^m If end of Cycle 2 (Day 28 ± 3 days) samples are obtained on Day 1 of Cycle 3, they must be obtained prior to CC-90009 administration. Additionally, bone marrow aspirates and biopsies may be obtained after a CR is confirmed, if relapse is suspected, or following treatment discontinuation to elucidate effects of long-term treatment or resistance mechanisms. Additional aspirates and biopsies will be collected as clinically indicated based on the Investigator's medical assessment.
- ⁿ For subjects that complete dosing in Cycle 4, performed/obtained once on Day 28 (± 3 days). For subjects that continue (after consultation with Medical Monitor) beyond Cycle 4, efficacy and bone marrow PD assessments may be obtained to confirm a CR, if relapse is suspected, or following treatment discontinuation to elucidate effects of long-term treatment or resistance mechanisms. Additional aspirates and biopsies will be collected as clinically indicated based on the Investigator's medical assessment. Refer to Section 6.3.2 and Section 6.4.
- ^o Predose blood sample for both intensive and sparse sampling schedule in Cycles 2-4. Refer to Sections 6.5 and 6.6.
- ^p Serum will be collected approximately every 6 months during study treatment and at EOT to be used for possible measurements of anti-SARS-CoV-2 serology (anti-SARS-CoV-2 total or IgG). Serum should also be collected approximately 4 weeks after a documented or suspected SARS-CoV-2 infection.

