2 STUDY OBJECTIVES AND ENDPOINTS

Table 2:Study Objectives

Primary Objectives

The primary objectives of the study are:

- To determine the safety and tolerability of CC-90009.
- To define the non-tolerated dose (NTD), the maximum tolerated dose (MTD) and/or the recommended Phase 2 dose (RP2D) of CC-90009.

Secondary Objectives

The secondary objectives are:

- To provide information on the preliminary efficacy of CC-90009 in R/R AML and R/R HR-MDS.
- To characterize the PK of CC-90009 in plasma and urine.

Exploratory Objectives

The exploratory objectives are:

- To explore the relationship between systemic exposure of CC-90009 and measures of toxicities, effectiveness, and PD biomarkers.
- To evaluate molecular and/or cellular markers in the bone marrow and blood that may be predictive of efficacy with CC-90009.
- To characterize the PK of hydroxypropyl-beta cyclodextrin in plasma and urine.
- To assess the impact of SARS-CoV-2 serologic status on subjects with R/R AML or HR-MDS receiving CC-90009.

Data from exploratory objectives may not be included in the Clinical Study Report.

Endpoint	Name	Description	Timeframe
Primary	Safety endpoints	DLTs, NTD, and MTD evaluated using the NCI CTCAE criteria, Version 4.03. Adverse events, including treatment-emergent adverse events (TEAEs), laboratory assessments, vital signs, ECG results, ECOG performance status, LVEF assessments, physical examinations, and vital signs.	Screening until 28 days after the last dose of CC 90009 for each subject during both dose escalation and expansion phases.
Secondary	Preliminary efficacy	Determined by response rates of AML by disease response criteria. Overall survival, relapse-free survival, progression-free survival, event-free survival, duration of remission, duration of response, and time to remission/response for AML subjects.	Dose escalation and dose expansion; throughout Treatment Period and the Follow-up Period (refer to Sections 6.3.2 and 6.3.3)
		Determined by response rates of HR-MDS by disease response criteria. Overall survival, relapse-free survival, progression-free survival, event-free survival, duration of remission, duration of response, time to AML transformation, and time to remission/response for HR-MDS subjects.	Dose escalation and dose expansion; throughout Treatment Period and the Follow-up Period (refer to Sections 6.3.2 and 6.3.3) of Part B only

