6.2.2 Adverse Event Monitoring

Adverse events (AEs) and serious adverse events (SAEs) will be recorded from the time a subject signs the ICD until 28 days after the last dose of CC-90009.

Subjects experiencing AEs will be monitored with relevant clinical assessments and laboratory tests, as determined by the Investigator (refer to Section 10 for detailed information). Every attempt will be made to document resolution dates for ongoing AEs. The AEs will be recorded on the AE page of the eCRF and in the subject's source documents.

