6.2.9 End of Treatment

An EOT evaluation (refer to Table 5, Table 7, Table 32, Table 34, Table 36, or Table 38 for procedures) will be performed for subjects who are withdrawn from treatment for any reason as soon as possible (≤ 28 days) after the decision to permanently discontinue treatment has been made. For subjects who complete dosing in Cycle 4, this visit should be completed on Day 28 (± 2 days) of Cycle 4.

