6.3 Follow-up Period

6.3.1 Safety Follow-up

All subjects will be followed for 28 days after the last dose of CC-90009 for AE reporting and concomitant medication information. The 28-day (\pm 3 days) safety follow-up contact may be by telephone. In addition, any SAEs made known to the Investigator at any time thereafter that are suspected of being related to CC-90009 will be reported as described in Section 10.1. Subjects will be followed for all SAEs and all AEs (SAEs and non-serious AEs) associated with confirmed or suspected SARS-CoV-2 infection until resolution, the condition stabilizes, the event is otherwise explained, the event is deemed irreversible, the subject is lost to follow-up, or for suspected cases, until SARS-CoV-2 infection is ruled-out.

Pregnancy testing will be performed per the PPP and Table 5, Table 7, Table 32, Table 34, Table 36, or Table 38.

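### The closing safety contact may fall up to 3 days before the 28-day AE window ends, and the End of Treatment visit has conflicting deadlines

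*Combined protocol and SAP*

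**What the plan says.** **Length of the window.** Table 3 (Section 2) gives the timeframe of the primary safety endpoint as "Screening until 28 days after the last dose of CC 90009 for each subject during both dose escalation and expansion phases". Section 6.2.2 says that AEs and SAEs "will be recorded from the time a subject signs the ICD until 28 days after the last dose of CC-90009", and Section 6.3.1 says "All subjects will be followed for 28 days after the last dose of CC-90009 for AE reporting and concomitant medication information". Sections 10.1 and 10.5 use the same limit and add that SAEs suspected to be drug-related are reported whenever they become known.

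**Closing contact.** Footnote c of Table 7 (Section 5) says "Safety Follow-up Visit is performed 28 days (± 3 days) after the last dose of CC-90009 for all subjects". The same footnote stands in Tables 5, 32, 34, 36 and 38, and the ± 3 days also appear in the Protocol Summary and in Sections 3.1 and 6.3.1. It may be a telephone call when no pregnancy test is due. In the tables, this column carries only AEs, concomitant medication and the pregnancy test.

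**End of Treatment (EOT).** Footnote b of the same tables sets three deadlines:

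- Early stoppers: "EOT Visit performed within 28 days after last dose of CC-90009 for subjects that discontinue prior to completing dosing in Cycle 4".
- Subjects who complete Cycle 4 dosing: Day 28 ± 2 of that cycle.
- Subjects treated beyond Cycle 4: within 28 days, counted from the last day of the *previous cycle*.

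Section 6.2.9 agrees on the second case. For anyone withdrawn from treatment for any reason, it asks for the visit "as soon as possible (≤ 28 days) after the decision to permanently discontinue treatment has been made". Section 7.2.12 lets treatment cycles be interrupted for up to 8 weeks.

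**The concern.** A visit that closes an observation window should not be allowed to come before the window ends. If the subject is telephoned on Day 25, nothing in the schedule prompts the site to ask about Days 26 to 28. Events on those days then depend on the subject or another hospital volunteering them. Non-serious events are the most exposed.

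The EOT visit matters for a different reason. It carries the last scheduled laboratory tests, ECG and LVEF, which Table 3 lists under the primary safety endpoint, and the last on-treatment marrow. With two starting points for its deadline, sites can make these measurements at quite different times while each follows a passage of the protocol. A subject who stops after a long hold is in deviation under one passage and compliant under the other.

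**Working it through.** The plan gives no figure to reproduce. The check is a day count, with all days counted from the last dose unless stated.

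**1. Range of the closing contact (footnote c).** Earliest 28 − 3 = Day 25; latest 28 + 3 = Day 31. After the earliest contact, 28 − 25 = 3 days of the window remain: Days 26, 27 and 28. As a share of days, 3/28 = 10.7%.

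**2. Does another scheduled AE evaluation fill the gap?** AE evaluation is also marked at EOT. For Cycle 4 completers, days after the last dose = cycle day − last dosing day, with cycle day 26 to 30 (28 ± 2):

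- Days 1-5: 26 − 5 = 21 to 30 − 5 = 25.
- Days 1-7: 26 − 7 = 19 to 30 − 7 = 23.

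EOT therefore falls at 19 to 25 days, before the window ends. Doses made up as late as Day 14, which Section 7.2.12 allows from Cycle 2, shorten this to 26 − 14 = 12 to 30 − 14 = 16. Early stoppers may have EOT at any time up to Day 28 under footnote b, so their visit need not reach Day 28 either. Long-term follow-up (Section 6.3.2) collects drug-related SAEs, not other AEs.

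**3. EOT deadline against the decision to stop.** For early stoppers the footnote b deadline is Day 28. An 8-week interruption is 56 days, and Section 7.2.12 does not say where the count starts, so two assumptions are shown:

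| Hold counted from | Decision, days after last dose | Past footnote b deadline | Latest EOT under 6.2.9 |
|---|---|---|---|
| Last dose | 56 | 56 − 28 = 28 days | 56 + 28 = 84 |
| Next cycle due on Day 29 (Days 1-7 schedule) | 29 + 56 − 7 = 78 | 78 − 28 = 50 days | 78 + 28 = 106 |

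Under either count, a decision later than Day 28 makes the footnote b deadline impossible to meet.

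**4. Beyond Cycle 4.** If *previous cycle* means the final cycle, EOT may fall (28 − 5) + 28 = 51 days after the last dose on Days 1-5, or (28 − 7) + 28 = 49 days on Days 1-7. If it means the cycle before, and the final cycle began the next day, the deadline is Day 28 of the final cycle: 28 − 5 = 23 or 28 − 7 = 21 days. The two readings differ by 28 days.

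**The case against.** The strongest reply is that the AE window is set by date and not by the contact. The investigator must record AEs to Day 28 whenever the call takes place. Under Section 10.5, every SAE with onset in that period is reportable once known, whatever its relationship to the drug, and suspected-related SAEs have no time limit. All of this stands. What remains is non-serious AEs, and SAEs the site never hears of, on at most three days and only after an early contact.

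EOT also includes an AE evaluation and, for some subjects, comes on or after Day 28. That is so, but not for Cycle 4 completers, and footnote b does not require it of early stoppers.

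The symmetric ± 3 days is stated consistently and is a legitimate scheduling choice. It does not contradict the 28-day recording rule. It only fails to guarantee a contact at the end of the period.

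On EOT, Section 5 refers readers to Section 6 for procedural detail, so Section 6.2.9 offers a workable rule for a stop during a hold. This limits the harm, and missing data are not shown. It does not remove the contradiction, because footnote b states its own deadlines without deferring to Section 6.2.9.

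**Conclusion.** The point holds as a minor matter of timing and consistency. The closing contact can precede the end of the 28-day window by up to 3 days, and for Cycle 4 completers no other scheduled AE evaluation reaches Day 28. The EOT deadlines in footnote b and Section 6.2.9 conflict, and the wording for subjects beyond Cycle 4 is ambiguous. The sizes in the EOT part depend on where the 8 weeks are counted from and on what *previous cycle* means.

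A reader might infer more, but the documents do not support it:

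- *The end of the safety window is not reliably observed.* Recording is fixed by date, SAEs stay reportable, and the gap arises only after early contacts.
- *About 11% of post-dose AEs could be missed.* The 10.7% is a share of days. Reading it as a share of events needs uniform onset and a Day 25 contact for everyone. Section 7.2.13.8 places hypotension on dosing days or within 24 hours of them, and Section 1.3.3 describes related non-hematologic toxicities as mostly arising during later dosing days and reversing quickly.
- *A Part B stopping boundary, such as 3 of 8 in Table 15, would change.* Nothing shows this. The rule is non-binding and counts DLT-type events, treatment-related AEs leading to reduction or discontinuation, and sepsis, while the events most exposed here are non-serious.
- *The EOT conflict shifts the AE window.* It does not; that window ends 28 days after the last dose. The conflict affects when the EOT measurements are made.
- *The pregnancy test may be done too early.* Footnote i says "Per the PPP, a pregnancy test is required 28 days after the last dose of for all FCBP", and the test sits at the ± 3-day visit, but its permitted window depends on the separate Pregnancy Prevention Plan and cannot be checked here.

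**What to change.** **Safety contact.** Set it to 28 (+3) days, not before Day 28, in the Protocol Summary, Sections 3.1 and 6.3.1, and the column header and footnote c of Tables 5, 7, 32, 34, 36 and 38. The stretch of the window left after the contact then falls from at most 3 days to 0. No visit or test is added. The downside is a narrower scheduling window: 4 calendar days (28 to 31) in place of 7 (25 to 31).

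**EOT visit.** In the same six tables, reconcile footnote b with Section 6.2.9 so that one starting point applies to subjects who stop before completing Cycle 4 dosing and to those treated beyond Cycle 4. State which cycle *previous cycle* means, if the phrase is kept. Leave the Cycle 4 Day 28 (± 2) visit as it is, because both passages share it and replacing it would create a new conflict.

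Counting from the decision removes the contradiction but can still place EOT well after Day 28 following a hold. The sponsor should therefore also say which EOT measurements count towards the 28-day safety endpoint. The cost is wording only.
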